### 7.3 LOST TO FOLLOW-UP

A participant will be considered lost to follow-up if he or she fails to be reached for follow-up surveys and study staff are unable to contact the participant after at least 5 attempts.

## 8 STUDY ASSESSMENTS AND PROCEDURES

## 8.1 ENDPOINT AND OTHER NON-SAFETY ASSESSMENTS

Data collection will be identical for both arms. Data will be obtained from caregiver enrollment interviews and 30- and 60-day interviews post-discharge, and from electronic health record (EHR) reviews encompassing the 60-day period post-hospitalization. Based on the pilot RCT, we estimate 10% of persons with late-stage ADRD will die during follow-up; caregiver interview data collection will proceed using a Bereavement Interview adaptation. Outcome measures will focus on 60-day interviews; 30-day interim interviews are necessary to support retention, ensure data capture for persons with ADRD who die, and for valid recall of hospital transfers (primary outcome) and secondary outcomes.

### **Family Caregiver Interviews:**

1. Emergency room visits + hospital admissions after discharge from index hospitalization
2. Use of hospice or community palliative care services
3. Patient symptom distress
  - a. Instrument: Symptom Management at the End of Life in Dementia (SM-EOLD)
  - b. Instrument: Neuropsychiatric Inventory Questionnaire (NPI-Q)
4. Shared decision-making about hospitalization
5. Shared decision-making about other burdensome treatments
6. Caregiver distress
  - a. Instrument: Family Distress in Advanced Dementia Scale
  - b. Zarit Burden scale, short form

### **Electronic Health Record Review:**

1. Symptom assessment and management plans during hospitalization-
  - a. Palliative Care Domain Index Items
2. Documented discussion of dementia prognosis
3. Documented discussion decision-making for goals of care
4. New nursing home transfers
5. Return to acute care – ED or Hospital readmissions within 60 days and up to 3 reasons for return

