## SCHEMA

## Flow Diagram

## 1.2 SCHEDULE OF ACTIVITIES

|  | Visit 1: During Hospitalization | Visit 2: During Hospitalization (Intervention) | Visit 3: PC Call 72 hours after discharge (Intervention) | Visit 4: PC Call 2 weeks after discharge (Intervention) | Visit 5 CRC interview 30 days post Hospitalization | Visit 6 CRC interview 60 days post hospitalization | CRC EHR Review post-60-day Hospitalization |
|--|---------------------------------|--|--|---|--|--|--|
| STUDY ENROLLMENT ACTIVITIES                                   |                                 |  |  |   |  |  |  |
| EHR Eligibility Screen   | X                               |  |  |   |  |  |  |
| Informed Consent   | X                               |  |  |   |  |  |  |
| Enrollment Baseline Assessment                                       | X                               |  |  |   |  |  |  |
| Randomization  | X                               |  |  |   |  |  |  |
| Control arm  | X                               |  |  |   | X  | X  | X  |
| ADRD-PC intervention arm   | X                               | X  | X  | X   | X  | X  | X  |
| DATA COLLECTION ACTIVITIES                                    |                                 |  |  |   |  |  |  |
| Hospital / ED transfers  |                                 |  |  |   | X  | X  | X  |
| Palliative Care Domain Index   |                                 |  |  |   |  |  | X  |
| Symptom Management at the End of Life in Dementia (SM-EOLD)          |                                 |  |  |   | X  | X  |  |
| Neuropsychiatric Inventory Questionnaire (NPI-Q)                     |                                 |  |  |   | X  | X  |  |
| Post-acute use of palliative care, hospice                           |                                 |  |  |   | X  | X  |  |
| New NH transition  |                                 |  |  |   |  |  | X  |
| Documented discussion of dementia prognosis                          |                                 |  |  |   |  |  | X  |
| Documented decision-making for goals of care                         |                                 |  |  |   |  |  | X  |
| Shared decision-making about hospitalization & burdensome treatments |                                 |  |  |   | X  | X  |  |
| Family Distress in Advanced Dementia scale                           |                                 |  |  |   | X  | X  |  |
| Zarit Burden scale   |                                 |  |  |   | X  | X  |  |

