## 5.2 EXCLUSION CRITERIA

Dyads will be excluded if (1) the LAR is not a family caregiver, (2) the patient currently receives palliative care or hospice, (3) patient or caregiver would be unduly stressed, or (4) dyad is not successfully randomized.

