#### 9.3 POPULATIONS FOR ANALYSES

N/A

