#### 9.4 STATISTICAL ANALYSES

##### 9.4.1 GENERAL APPROACH

**Analysis:** Descriptive analyses of variables will examine distributions, influential data points, and missing data. Means (standard deviations) will be reported for continuous variables and frequencies (percentages) for categorical variables. Continuous variables (e.g., PC Domain Index, etc) that are poorly distributed may be transformed or analyzed using non-parametric

tests. We anticipate missing data on independent variables will be minimal. We will use simple mean and mode imputation for those variables included in regression models if less than 5% of patients have missing data; else, conditional (i.e., regression) imputation will be used. Available case analysis will be conducted for 30-day outcomes. Missing 60-day dichotomous outcomes will be multiply imputed if missingness exceeds 10%. Caregiver data collection is completed after deaths as in our prior ADRD research. Primary analysis will use intention-to-treat analysis. We will evaluate the effectiveness of randomization by comparing intervention and control participants on baseline measures. Variables that are not equally distributed between arms could potentially bias results. We will include these variables in each initial model and use a change-in-effect method for determining whether they are confounders. If removing any of these variables from the model does not appreciably change the regression coefficient estimate of the intervention group variable, we will not need to include them in the final model. Given our randomized design, we anticipate little confounding. A priori exploratory analyses will examine effects by sex as a biological variable, race / ethnicity, and GDS stage.

---

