#### 9.4.3 ANALYSIS OF THE SECONDARY ENDPOINT(S)

**Aim 2:** To compare patient-centered secondary outcomes between intervention and control arms: a) symptom treatment (Palliative Care Domain index); b) symptom control (Symptom Management at the End of Life in Dementia scale, Neuropsychiatric Inventory Questionnaire); c) post-acute use of palliative care or hospice; and d) transition to nursing home care.

Analysis to Meet Aim 2: We will compare study arms during 60 days post-discharge on the following outcomes:

2.a. Symptom treatment: This ordinal outcome is the summation of presence (=1) or absence (=0) of 10 domains of palliative care. We will treat it as a continuous variable due to a high variation observed in the pilot data. We will use Student's t-test to compare the mean difference between study arms unless violation of assumptions warrants the Mann-Whitney test. We will use a multiple linear regression model with main effects for treatment group, study site, GDS Stage and patient and caregiver sex as a biological variable.

2.b. Symptom control: We will use Symptom Management (SM-EOLD) scale to measure caregiver report of patients' uncontrolled symptom distress and Neuropsychiatric Inventory Questionnaire (NPI-Q) to measure caregiver report of patients' neuropsychiatric symptom distress. Linear mixed models with random intercepts for patients will be used with a time indicator (30 vs 60 days follow-up) with the above main effects.

2.c. Use of post-acute palliative care or hospice: This outcome will be defined by whether patients ever use hospice or outpatient palliative care during the time from discharge to 60 days follow-up. We will compare the proportions using Pearson's chi-square test. Logistic regression will be used for multivariable modeling with the same main effects as in Aim 2.a. Final estimates will be reported as covariate-adjusted odds ratios.

2.d. Transition to nursing home care: This outcome will be defined by whether patients transition to nursing home care during the time from discharge to 60 days follow-up. We will compare proportions using Pearson's chi-square test. Logistic regression will be used for multivariable modeling with the same main effects as in Aim 1. Final estimates will be reported as covariate-adjusted odds ratios.

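### New nursing home transition (H2d) has the hospital EHR as its only source and no defined at-risk set; a residence item in the existing caregiver interviews and a definition of *new* would repair both

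*Combined protocol and SAP*

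**What the plan says.** **Source.** Section 8.1 puts "New nursing home transfers" in its EHR list; none of the six caregiver interview items concerns residence. In the section 1.2 schedule the row "New NH transition" has one mark, under the EHR review after day 60. The row "Hospital / ED transfers" is marked at both interviews and at the EHR review, and post-acute palliative care or hospice use is marked at both interviews. Section 8.1 also gives recall of secondary outcomes as a reason for the 30-day interview, but names no nursing home item.

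**Definition.** The aims and H2d speak of *new* transitions. Section 9.4.3 (2.d) defines the outcome as "whether patients transition to nursing home care during the time from discharge to 60 days follow-up", without *new* and without a restriction on who is at risk.

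**Population.** Section 5.1 does not require community residence. Section 5.2 begins "Dyads will be excluded if (1) the LAR is not a family caregiver, (2) the patient currently receives palliative care or hospice", and neither of its two remaining exclusions concerns residence. Section 9.3, "POPULATIONS FOR ANALYSES", is marked not applicable, and section 9.4.1 states: "Primary analysis will use intention-to-treat analysis".

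**Contact and masking.** Section 6.1 provides two post-discharge calls by the palliative care team, in the intervention arm only. H1 (section 9.1) expects fewer transfers in that arm. Section 6.3 masks the interviewers to arm but acknowledges that the EHR will show the intervention encounters.

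**The concern.** The other outcomes taken only from the EHR (Palliative Care Domain Index, documented prognosis discussion, documented goals-of-care decisions) are about documentation, so the EHR is their natural source. A move into a nursing home after discharge happens in the community. It is the only outcome of that kind with no caregiver source.

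A hospital record may not learn of a later move unless the patient returns or the team makes contact. The calls could raise recording in the intervention arm; fewer returns, if H1 is true, could lower it. Section 9.4.1 imputes missing binary outcomes when missingness exceeds 10%, but no rule says how an EHR silent on residence is coded. If silence is coded as no transition, missed moves never count as missing and imputation cannot reach them.

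The denominator is a second, independent gap. A patient who already lives in a nursing home cannot make a new transition. If such patients are enrolled and stay in 2.d, they dilute the difference.

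**Working it through.** **1. The plan's own figure.** Table 3 gives control 33%, difference 15 points, power 0.82 at n = 180 per arm and 0.78 at n = 159 (424 × 0.85 = 360 and 424 × 0.75 = 318 in total). I used the two-proportion test, two-sided 0.05:

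power = Φ[(d − 1.96·SE0)/SE1], with SE0 = √(2p̄(1−p̄)/n) and SE1 = √((p1(1−p1) + p2(1−p2))/n).

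- 33% vs 48%: 0.829 (n = 180) and 0.780 (n = 159), which agrees with Table 3.
- 33% vs 18%, the direction of H2d: SE0 = 0.0459, SE1 = 0.0453, power 0.907 (n = 180) and 0.870 (n = 159).

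The row therefore reproduces as an increase. Below I use 33% vs 18%, because H2d predicts a decrease.

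**2. Capture, with no true effect.** Inputs from the documents: 33% (here set in both arms), n = 180, control transfer rate 0.53, and 0.53 − 0.25 = 0.28 in the intervention arm (Table 3). Assumptions: any-return probability is 1 − exp(−rate); a move is always captured if the patient returns and with probability c otherwise; the calls have no effect on capture.

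- Any return: 1 − exp(−0.53) = 0.411 and 1 − exp(−0.28) = 0.244.
- Sensitivity = r + (1 − r)c; observed rate = 0.33 × sensitivity.

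| c | Sensitivity, control / intervention | Observed, control / intervention | Odds ratio | False-positive rate (both tails) |
|---|---|---|---|---|
| 0.8 | 0.882 / 0.849 | 29.1% / 28.0% | 0.95 | 0.042 + 0.014 = 0.056 |
| 0.6 | 0.765 / 0.698 | 25.2% / 23.0% | 0.89 | 0.071 + 0.007 = 0.078 |
| 0.4 | 0.647 / 0.547 | 21.3% / 18.0% | 0.81 | 0.121 + 0.003 = 0.124 |

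With the smaller Table 3 effect (0.53 − 0.20 = 0.33) the odds ratios are 0.96, 0.91 and 0.85. In this model the bias favours H2d; better recording through the intervention-only calls would push the other way.

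**3. Denominator.** Assumptions: 33% and 18% apply to patients at risk, and a share f of each arm already lives in a nursing home. The documents do not give f.

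- Residents kept as non-events: rates 0.33(1−f) and 0.18(1−f) at n = 180. For f = 0.2: 0.264 vs 0.144, power 0.809.
- Restricted to at-risk patients: 33% vs 18% at n = 180(1−f). For f = 0.2: n = 144, power 0.835.

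| f | Residents kept as non-events | Restricted |
|---|---|---|
| 0 | 0.907 | 0.907 |
| 0.1 | 0.864 | 0.876 |
| 0.2 | 0.809 | 0.835 |
| 0.3 | 0.741 | 0.780 |
| 0.4 | 0.661 | 0.718 |

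Restriction never does worse than keeping residents as non-events, but it stays below the undiluted 0.907.

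**The case against.** **Arm-dependent capture is inferred.** The documents do not describe how far the EHR review reaches or how residence is abstracted. A direct discharge to a facility would normally be in the index record in both arms. Fewer returns is only a hypothesis; the calls end by week 2 of a 60-day window, and section 6.1 does not say they are charted. All of this stands. A reader might infer that 2.d is known to be biased by arm, or biased in a known direction; the documents do not support that.

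**The presence of residents is not shown.** No count is given, and the contents of the baseline assessment are not itemised, so prior residence may already be recorded. That stands too: what is established is that eligibility admits residents and 2.d does not remove them.

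**The word *new* survives elsewhere.** It is in the aims, H2d, the schedule and the abstraction item. A reader might infer that residents returning to their facility will be counted as transitions. With f = 0.2 that gives 0.2 + 0.8 × 0.33 = 0.464 vs 0.2 + 0.8 × 0.18 = 0.344, and power of about 0.64 to 0.65 (pooled or unpooled variance). An abstractor recording new transfers would not naturally do this, so it is the less plausible branch.

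**The 33% may already be diluted.** If it is an all-patient pilot rate, imperfect capture and residents may be in it already, and discounting it again would double-count. The documents do not say, so the figures in steps 2 and 3 are illustrations.

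**Interviews have weaknesses.** Caregivers are not masked (section 4.1), and interviews suffer dropout. This stands, but the interviewers are masked, whereas the EHR reviewer can see the arm.

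**Conclusion.** The point holds as a design improvement to one secondary outcome; the primary outcome has both interview and EHR sources. Three things are read directly from the documents: the EHR is the sole source, nursing home residents are not excluded, and no at-risk set is defined.

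Under-recording of moves after discharge, and its dependence on arm, is a plausible risk whose direction and size cannot be determined. Under the return-based model it is negligible if capture without a return is high (false-positive rate about 0.06 at 80%) and material if it is low (about 0.12 at 40%). The denominator gap costs about 0.03 in power at an assumed 20% resident share (0.81 vs 0.84) and more at higher shares. With the fix so small, the change should be made.

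**What to change.** 1. Add current residence and the date of any nursing home admission to the 30-day, 60-day and bereavement interviews, and make this the main source for 2.d. Keep the EHR as a supplement.
2. Treat unknown residence as missing, not as no transition, so that the imputation rule in section 9.4.1 applies.
3. Record residence before the index admission. Define *new* in 2.d, stating whether a direct discharge to a nursing home counts.
4. Restrict 2.d to patients not living in a nursing home before the index admission, and enter that set in section 9.3.

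**Cost.** One interview item, including the Spanish and bereavement versions, and an IRB amendment. Interview non-response applies (the plan projects 15% to 25% dropout), and where the EHR fills a gap the capture question remains for those dyads. The denominator is smaller: power falls below the undiluted n = 180 figure (0.835 against 0.907 at a 20% resident share), but not below that of the analysis that keeps residents as non-events (0.809).

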## 8.2 SAFETY ASSESSMENTS

The Principal Investigator and research team will comply with the University of North Carolina Office of Human Research Ethics (OHRE) requirements and consistent with DHHS 45 CFR part 46 and NIA guidelines for defining, collecting and reporting any unanticipated problems, adverse events or serious adverse events during the conduct of research.

This study uses a single IRB (University of North Carolina-Chapel Hill) to conduct ethical review required for the protection of human subjects. The study is a multi-site clinical trial, and the participating sites will utilize a single protocol and have agreed to the single IRB oversight structure.

All study procedures, informed consent forms, and recruitment procedures will undergo review by the Institutional Review Board at the University of North Carolina-Chapel Hill prior to initiating research, and will be subject to annual and other required reviews. Enrolled participants will be dyads of persons with late-stage ADRD and their family caregivers; caregivers will provide written informed consent for dyad participation. Investigators will work with NIA to convene a

Data Safety and Monitoring Board to oversee the human subjects' safety and adverse event reporting for this multi-site clinical trial.

## 8.3 ADVERSE EVENTS AND SERIOUS ADVERSE EVENTS

### 8.3.1 DEFINITION OF ADVERSE EVENTS

Adverse events (AE) are defined as

- Any untoward or unfavorable medical occurrence in a human study participant, including any abnormal sign (e.g. abnormal exam or laboratory finding), symptom or disease temporally associated with the participants' involvement in the research, whether or not considered related to participation in the research.
- *In the ADRD-PC study tracked AEs will include major emotional distress for family caregivers, and confidentiality risk events for the person with ADRD.*

### 8.3.2 DEFINITION OF SERIOUS ADVERSE EVENTS

Serious adverse events (SAE) are defined as

- Death
- Life-threatening health events
- Acute illness causing hospitalization
- Health event causing persistent new disability or incapacity, or
- Similar significant hazardous events
- *In the ADRD-PC study these events will be tracked for all participants. These events are expected health outcomes for people with ADRD and may also occur for family caregivers. SAEs will be included in study data collection but will not be included in AE reporting; see explanation below.*

### 8.3.3 CLASSIFICATION OF AN ADVERSE EVENT

#### 8.3.3.1 SEVERITY OF EVENT

For adverse events (AEs), the following guidelines will be used to describe severity.

- **Mild** – limited in intensity and duration, without sustained effect on participant
- **Moderate** – limited in intensity or in duration, with some sustained effect on participant
- **Severe** – significant intensity and duration of event, with significant sustained effect on participant

#### 8.3.3.2 RELATIONSHIP TO STUDY INTERVENTION/EXPERIMENTAL MANIPULATION

All adverse events (AEs) will have their relationship to study procedures, including the intervention, assessed by an appropriately-trained clinician based on temporal relationship and his/her clinical judgment. The degree of certainty about causality will be graded using the categories below.

- **Definitely Related** – There is clear evidence to suggest a causal relationship, and other possible contributing factors can be ruled out. The clinical event, including an abnormal laboratory test result, occurs in a plausible time relationship to study procedures administration and cannot be explained by concurrent disease or other drugs or chemicals. The response to withdrawal of the study procedures should be clinically plausible. The event must be pharmacologically or phenomenologically definitive.
- **Probably Related** – There is evidence to suggest a causal relationship, and the influence of other factors is unlikely. The clinical event, including an abnormal laboratory test result, occurs within a reasonable time after administration of the study procedures, is unlikely to be attributed to concurrent disease or other drugs or chemicals, and follows a clinically reasonable response on withdrawal.
- **Potentially Related** – There is some evidence to suggest a causal relationship (e.g., the event occurred within a reasonable time after administration of study procedures). However, other factors may have contributed to the event (e.g., the participant's clinical condition, other concomitant events). Although an AE may rate only as "possibly related" soon after discovery, it can be flagged as requiring more information and later be upgraded to "probably related" or "definitely related", as appropriate.
- **Unlikely to be related** – A clinical event, including an abnormal laboratory test result, whose temporal relationship to study procedures administration makes a causal relationship improbable (e.g., the event did not occur within a reasonable time after administration of the study procedures) and in which other drugs or chemicals or underlying disease provides plausible explanations (e.g., the participant's clinical condition, other concomitant treatments).
- **Not Related** – The AE is completely independent of study procedures administration, and/or evidence exists that the event is definitely related to another etiology. There must be an alternative, definitive etiology documented by the clinician.]

#### 8.3.3.3 EXPECTEDNESS

An investigator team member with expertise in advanced dementia and palliative care will be responsible for determining whether an adverse event (AE) is expected or unexpected. An AE will be considered unexpected if the nature, severity, or frequency of the event is not consistent with the risk information previously described for the study procedures.

#### 8.3.4 TIME PERIOD AND FREQUENCY FOR EVENT ASSESSMENT AND FOLLOW-UP

The occurrence of an adverse event (AE) or serious adverse event (SAE) may come to the attention of study personnel during study visits and interviews of a study participant presenting for medical care, or upon review by a study monitor. Any medical or psychiatric condition that is present at the time that the participant is enrolled will be considered as baseline and not reported as an AE.

All AEs, not otherwise precluded per the protocol, will be captured on the appropriate case report form (CRF). All AEs occurring while on study will be documented appropriately regardless of relationship. At each study visit, the investigator will inquire about the occurrence of AE/SAEs since the last visit. Events will be followed for outcome information until resolution or stabilization.

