The primary risk for family caregivers is potential emotional distress related to learning more about dementia prognosis and participation in goals of care decisions. Participation in the study, particularly in the intervention group, may draw family members' attention to ADRD as a serious and progressive illness, and ask them to consider the pros and cons of different treatment options. This risk is no greater than a similar risk encountered in all current healthcare involving hospital care for persons with late-stage ADRD and the varied treatment choices confronting their family caregivers. However, given the vulnerable characteristics of persons with ADRD and the level of strain documented for ADRD caregivers, training of site-based research staff and investigators will explicitly address this potential risk.

- To protect against emotional distress for the family caregiver, we will inform them of their right to skip interview items, pause during participation, or withdraw from the study at any time. During the course of data collection, the CRC may identify clinical concerns or extreme emotional distress expressed by the family caregivers. The Principal Investigator, Site-PI or other senior investigator will be available to provide timely guidance for response to these concerns.

All CRCs will be trained to notify Site-PIs for any caregiver who expresses extreme emotional distress in response to study participation activities such as consent or interview items, or scores  $> 4.1$  points average / 37 points summed score (one standard deviation above the mean) on the Emotional Distress Subscale of the Family Distress in Advanced Dementia scale. The instrument has construct validity established with correlation to depression scoring instruments. CRCs will follow-up with caregivers with a script asking about their access to current emotional support, and desire for additional access to mental health resources. If the caregiver expresses need for additional mental

health resources, the CRC will contact the Site-PI, who will assist the CRC in exploring level of need and identification of appropriate referral resources, which may include the family caregiver's primary care provider, the current hospital attending physician and social worker, or local mental health services.

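### Asking about adverse events at every study visit means, read literally, five inquiries after enrollment in the intervention arm and two in control, which may inflate the intervention arm's AE counts

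*Combined protocol and SAP*

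**What the plan says.** Section 8.3.4 sets the inquiry rule: "At each study visit, the investigator will inquire about the occurrence of AE/SAEs since the last visit". It makes no exception by arm or by type of visit.

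Section 1.2 numbers six visits. Three column headings carry an intervention label (closing bracket omitted here): "Visit 2: During Hospitalization (Intervention", "Visit 3: PC Call 72 hours after discharge (Intervention" and "Visit 4: PC Call 2 weeks after discharge (Intervention". The later contacts, "Visit 5 CRC interview 30 days post Hospitalization" and "Visit 6 CRC interview 60 days post hospitalization", are marked for both arms, as are Visit 1 and the EHR review after day 60. The schedule has no row for adverse events.

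Section 6.1 gives the two post-discharge calls to a palliative care team member, possibly helped by a site CRC. The calls are meant to draw out concerns and give emotional support. Section 8.3.1 names two tracked AEs: major emotional distress in caregivers and confidentiality events. On caregiver distress, section 2.3.1 says: "Participation in the study, particularly in the intervention group, may draw family members' attention to ADRD as a serious and progressive illness".

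The DSMB assesses safety data from each arm at least twice a year (section 10.1.6) and receives AE summaries every six months (section 8.3.6). Section 9 plans no between-arm analysis of adverse events.

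**The concern.** The number of times a dyad is asked about adverse events depends on its arm. The extra contacts fall in the arm where the protocol expects caregiver distress to be more likely, and two of them are calls designed to bring concerns to the surface. They are also run by clinicians who know the allocation, whereas the interviewers at 30 and 60 days are masked (section 6.3).

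If sites follow section 8.3.4 as written, more distress AEs in the intervention arm could reflect more harm, more asking, or both. Nothing in the plan records the contact at which an event was learned of, so the explanations could not be separated later. The DSMB would be reading these counts, and section 7.1 asks it to consider whether any stopping rules should be based on AE reporting.

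**Working it through.** The plan gives no figure to reproduce. The check is a count followed by an illustration on assumed values.

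**Count (section 1.2).** Numbered visits: intervention 1 to 6, six in all; control 1, 5 and 6, three in all. After enrollment at Visit 1: five against two, or 5/2 = 2.5 times as many. Each arm also has one EHR review.

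**Illustration.** Let r be the true risk of an event, equal in both arms, and d the chance that one inquiry brings out an event that has happened and is not yet recorded. With m inquiries, the proportion of dyads with a detected event is r × [1 − (1 − d)^m], with m = 5 (intervention) or m = 2 (control). The ratio does not depend on r. Both r and d are assumptions.

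The table uses r = 10% and 424/2 = 212 dyads per arm, leaving out the 50 supplement dyads. The last column is the chance of a nominally significant excess in the intervention arm on a two-sided 0.05 comparison of proportions. No such test is planned; the column only gives scale.

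| d | Intervention | Control | Ratio | Difference (points) | Chance of spurious excess |
|---|---|---|---|---|---|
| 0.3 | 8.3% | 5.1% | 1.63 | 3.2 | 26% |
| 0.5 | 9.7% | 7.5% | 1.29 | 2.2 | 12% |
| 0.7 | 10.0% | 9.1% | 1.10 | 0.9 | 5% |
| 0.9 | 10.0% | 9.9% | 1.01 | 0.1 | 3% |
| 1.0 | 10.0% | 10.0% | 1.00 | 0.0 | 2.5% |

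Example at d = 0.3: 1 − 0.7^5 = 0.832, 1 − 0.7^2 = 0.510, and 0.832/0.510 = 1.63. At d = 0.3 the chance in the last column is 15% for r = 5% and 49% for r = 20%. As d falls toward zero the ratio approaches 5/2 = 2.5.

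**Timing.** The table applies to an event present before Visit 2 that every later inquiry can still bring out. Later events have fewer extra chances. At d = 0.3:

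- between Visits 2 and 3, four against two: (1 − 0.7^4)/(1 − 0.7^2) = 0.760/0.510 = 1.49
- between Visits 3 and 4, three against two: 0.657/0.510 = 1.29
- after Visit 4, the same number in each arm: 1.00

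For a given d, events spread over the 60 days would therefore give a smaller overall ratio than the table.

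**What does not depend on the visit count.** The Family Distress and Zarit scales are scheduled at Visits 5 and 6 in both arms, so the subscale cut-off for caregiver distress in section 2.3.1 is applied equally. Returns to hospital are captured by interview and EHR review in both arms (section 8.1), and the same contacts bring out deaths.

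**After the change below.** Two scripted inquiries per arm give m = 2 in both, and a ratio of 1.00 for any d in this model.

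**The case against.** The strongest reply is that inquiry at Visits 2 to 4 is an inference. Section 8.3.4 has the investigator asking, while Visit 2 is a clinical consultation, Visits 3 and 4 are supportive calls, and the schedule marks no data collection at any of them. Sites may never ask there. This stands as a reason to write may be inflated rather than is biased. It does not remove the problem, because the rule covers every study visit and these contacts are numbered as visits.

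Second, the inquiry looks back to the last visit, so the control arm's 30-day inquiry covers the same calendar time. This also stands in part: with full recall the ratio is 1.00. But section 8.1 itself relies on the 30-day interview for valid recall of hospital transfers, so complete recall of passing distress cannot be taken for granted.

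Third, AE reporting is to be refined with the DSMB at its first meeting (section 8.3.5), and the DSMB's data elements are to be defined then (section 10.1.6). That is a suitable place to settle the matter, but neither section mentions inquiry points or look-back.

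A reader might also infer three stronger points that the documents do not support:

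- **A more than twofold excess.** Giving each inquiry the same independent chance of a fresh event, say 5%, yields 1 − 0.95^5 = 22.6% against 1 − 0.95^2 = 9.8%, a ratio of 2.3. That ignores the look-back and gives one arm more event opportunity over the same calendar time.
- **A flat contradiction with "Data collection will be identical for both arms".** That sentence is in section 8.1, which covers endpoint and other non-safety assessments. It does not clearly govern AE inquiry.
- **Bias in the caregiver distress outcomes.** Those scales are measured at the same times in both arms.

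**Conclusion.** The point holds as a risk of unequal ascertainment of adverse events, chiefly caregiver distress, in the safety data that the DSMB reviews by arm. Read literally the rule gives five inquiries against two, and any distortion from the count runs toward more events in the intervention arm.

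Its size cannot be fixed from the documents. With equal true risk, the ratio for early events is about 1.6 at 30% detection per inquiry, 1.3 at 50%, 1.1 at 70% and 1.0 at full recall, and lower when events arise later. This assumes independent inquiries with the same detection chance, each able to recover any earlier event. If an event missed at one inquiry were never asked about again, each would have a single scripted chance in both arms, and any difference would come from the shorter recall interval in the intervention arm.

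It would go too far to say that a treatment comparison is biased. No AE comparison is planned in section 9, the distress outcomes and the scale-based trigger are symmetric, and section 8.3.2 keeps SAEs outside AE reporting. An effect on stopping is also speculative, since section 7.1 sets no stopping rules. This is a cheap improvement, not a flaw in the primary or secondary analyses.

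**What to change.** In section 8.3.4, with a matching row in the Schedule of Activities:

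1. Make the 30-day and 60-day interviews the scripted AE inquiry points in both arms, with the same question. Fix the look-back: since enrollment at 30 days, and since the 30-day interview at 60 days, whatever contacts occurred in between. Without this, the 30-day question would reach back only to Visit 4 in the intervention arm but to Visit 1 in control, reversing the imbalance.
2. Continue to record and report every AE whenever it is learned of.
3. Add a field for the contact at which the event was learned of. An entry naming Visits 2 to 4 reveals the arm, and site PIs report AEs to the overall PI (section 8.3.5), who is to stay masked (section 6.3). Keep the field from the masked PI.
4. Give the DSMB and the final report a table by arm restricted to the common contacts (both interviews and the EHR review), beside the table from all sources. List separately the events learned of only at Visits 2 to 4.

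The cost is one CRF field, one extra table and a short addition to the text; no visits are added. The common-contact table may miss distress voiced only at intervention contacts, including during the in-hospital discussions of prognosis and goals of care. That is why the all-source table must stay beside it.
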